5.6.7. Other Ocular Exams

Ocular symptoms, comfort grading assessment, ophthalmoscopy findings, and slit lamp biomicroscopy results will be categorically summarized.

Slit Lamp Biomicroscopy:

The distribution of Bulbar Conjunctival Injection, Sclera – Ciliary Flush, and Corneal Edema over the following categories: Absent, Mild, Moderate, and Severe for each treatment at each visit will be described by the frequencies in each category for each active dosing regimen and its matching vehicle placebo in [Tables 14.3.6.6 -14.3.6.8](#).

All subjects' slit lamp biomicroscopy information will be presented in [Listing 16.2.9.3](#).

Inflammation Endpoints:

As mentioned in Section 5.3.2, although the [Tables 14.2.2.1, 14.2.3.1, 14.2.3.2, 14.2.3.3](#), and [14.2.5.1](#) are listed with other efficacy endpoint tables, the analyses of the eye exam parameters at the Screening and EOS visits, especially those for the non-study-eye, are primarily considered as safety analyses.

Dilated Indirect Ophthalmoscopy:

	Document Number: CLN.001.SAP	Version: 0
	Document Title: Clinical Study CPN-201 Statistical Analysis Plan	Page 26 of 35

The number of subjects with abnormal vitreous retina, macula, choroid, and optic nerve for each active dosing regimen and its matching vehicle placebo will be summarized for Screening and EOS visits in [Table 14.3.6.9 – 14.3.6.13](#).

Cup-to-Disc Ratio will be summarized by mean, SD, 95% CI, median, Q1, Q3, minimum, and maximum for each active dosing regimen and its matching vehicle placebo at Screening and EOS visits in [Table 14.3.6.14](#).

Lens pathology findings for non-study eye will be summarized in [Table 14.3.6.15](#) for subjects with phakic lens by the total number of subjects with abnormal findings and by abnormal cataract category: Nuclear, Cortical, and Posterior Subcapsular and by cataract Grade 1, 2, and 3 for each active dosing regimen and its matching vehicle placebo at Screening and EOS visits.

All dilated indirect ophthalmoscopy ocular exam data will be presented in [Listing 16.2.9.4](#).

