2. STUDY OBJECTIVES AND ENDPOINTS

The objectives and corresponding study endpoints are depicted in Table 4 below.

Table 4: Study Objectives and Endpoints

Objectives	Endpoints
The primary safety objective of this study is to investigate the safety and tolerability of APP13007 versus corresponding matching vehicle placebo for the treatment of inflammation and pain through POD22 in Part A and POD15 in Part B after cataract surgery.	
• Early Treatment Diabetic Retinopathy Study (ETDRS) Best corrected Visual Acuity by pinhole method• Slit-lamp biomicroscopy• Change from baseline to each post-surgery visit in ocular signs:
○ Corneal edema○ Ciliary flush○ Bulbar conjunctival injection• Dilated indirect ophthalmoscopy• Intraocular pressure (IOP)• Adverse event (AE) monitoring• Clinical chemistry and hematology parameters (Appendix A)• Blood cortisol concentrations
The primary efficacy objective of this study is to investigate the preliminary efficacy of APP13007 versus matching vehicle placebo for the treatment of inflammation and pain through POD15 after cataract surgery.	
• Anterior chamber cell (ACC) count at POD15• Pain grade on POD15
The secondary efficacy objective of this study is to compare the effects on markers of inflammation and pain and visual acuity between active APP13007 and matching vehicle placebo for each dose strength and frequency.	
• Anterior chamber cell (ACC) count at PODs 4, 8, and 22/EOT (Part A) and PODs 4 and 8 (Part B).• Pain grade on PODs 4, 8, and 22/EOT (Part A) and PODs 4 and 8 (Part B)• Anterior chamber flare (ACF) grade on PODs 4, 8, 15 and 22/EOT (Part A) and PODs 4, 8 and 15/EOT (Part B)• Use of rescue medication prior to each visit• Proportion of subjects with ACC count = 0 at PODs 4, 8, 15 and 22/EOT (Part A) and PODs 4, 8 and 15/EOT (Part B) without receiving rescue medication;• Proportion of subjects who are pain-free at PODs 4, 8, 15 and 22/EOT (Part A) and PODs 4, 8 and 15/EOT (Part B)

	
15/EOT (Part B) without receiving rescue medication;
 
• Proportion of subjects with flare grade = 0 at PODs 4, 8, 15 and 22/EOT (Part A) and PODs 4, 8 and 15/EOT (Part B) without receiving rescue medication• Visual acuity (ETDRS Best corrected Visual Acuity by pinhole method)
--	---

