10.3.3. Analysis of Safety

Analysis of safety data will be performed for all subjects in the Safety Population.

Adverse events (AE) will be summarized by total number of any AE, number of subjects reporting the AE, ocular AEs (affecting the study eye and/or the non-study eye and/or both eyes, when appropriate), ocular TEAEs in the study eye, systemic AEs, SAEs, suspected unexpected serious adverse reaction (SUSARs), discontinuing study drug due to an AE, by relationship to study drug and/or ocular surgical procedure, and by severity. Adverse events will be coded using Medical Dictionary for Regulatory Activities (MedDRA, most current version) and categorized by system organ class and preferred terms.

The analyses of IOP will include the summary statistics of IOP and its change from baseline (POD1/pre-dose) at each visit, the proportion of subjects with an IOP ≥ 24 mmHg AND an increase ≥ 10 mm Hg from pre-dose baseline, and the proportion of subjects with an IOP > 30 mmHg at any time following initiation of study drug.

The proportion of subjects with a visual acuity worsening from POD1/pre-dose visit of ≥ 2 lines will also be summarized.

Ocular symptoms, comfort grading assessment, ophthalmoscopy findings, and slit lamp biomicroscopy results will be categorically summarized.

Details of statistical analyses will be included in the SAP.

10.3.4. Interim Analysis:

No interim analyses are planned for this study.

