5.1.5. Visits, Days, PODs, EOT and EOS

5.1.5.1. Definition of Visits

Based on [Tables C1 and C2](#), Schedule of Events, visits and their nominal days relative to the surgery are further described in [Table E](#) below.

	Document Number: CLN.001.SAP	Version: 0
	Document Title: Clinical Study CPN-201 Statistical Analysis Plan	Page 14 of 35

Table E: Visits

Visit Number	Visit Name	Notes
10	Screening	Days -28 to -1. Baseline for most safety endpoints
20	Surgery	Day 0
30	POD1	Randomization and start of study drug. Baseline for efficacy endpoints
40	POD4	3-5 days post-surgery
50	POD8	7-9 days post-surgery
60	POD15 (Part A only)	14 -16 days post-surgery for Part A
70	End of Treatment (EOT) POD22 (Part A) POD15 (Part B)	1-2 days post last dose of study drug. Part A: 22-23 days post-surgery Part B: 15-16 days post-surgery
80	End of Study (EOS) POD28 (Part A) POD22 (Part B)	6-8 days post the last dose of study drug. Part A: 27-29 days post-surgery. Part B: 20-22 days post-surgery
90	UNSCHEDULED	

Some subjects may discontinue their study drug before the scheduled EOT. Situations like this will be discussed in the following sections.

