5.1.7. Baseline Definitions

Baseline is the last observed (without LOCF or any other imputation) assessment prior to the time when the first dose of study drug is administered unless otherwise specified.

Screening will be considered as the baseline for the Screening vs EOS comparison. EOS data will be summarized with Screening data in the same table.

For all other PODs, i.e., POD 1, 4, 8, 15, and 22 (for Part A), POD1, 4, 8, and 15 (for Part B), ocular examinations are carried out for the study eye only. These data will be summarized in the same table for each active dosing regimen and its matching vehicle placebo. The Pre-dose assessment at POD1 will be the baseline.

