6.6. Changes to Protocol-Planned Analyses

- Added analyses for ACC grade at PODs 4, 8, 15 (and 22 for Part A).

	Document Number: CLN.001.SAP	Version: 0
	Document Title: Clinical Study CPN-201 Statistical Analysis Plan	Page 28 of 35

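### The SAP gives no change-from-baseline or shift summary for corneal edema, ciliary flush and conjunctival injection, which the protocol lists as a safety endpoint, and does not declare the difference

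*SAP*

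**What the plan says.** Protocol Section 2, Table 4 (repeated in the synopsis) lists under the primary safety objective "Change from baseline to each post-surgery visit in ocular signs", naming corneal edema, ciliary flush and bulbar conjunctival injection. This bullet is separate from the one for slit-lamp biomicroscopy.

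The protocol's analysis section is less specific. Section 10.3.3 says: "Ocular symptoms, comfort grading assessment, ophthalmoscopy findings, and slit lamp biomicroscopy results will be categorically summarized". It leaves the details to the SAP.

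SAP 1.2 (Table A) and SAP 5.6 keep the three signs as sub-items of slit-lamp biomicroscopy, without the change-from-baseline wording. SAP 5.6.7 plans that the distribution of each sign "over the following categories: Absent, Mild, Moderate, and Severe for each treatment at each visit will be described by the frequencies in each category" (Tables 14.3.6.6 to 14.3.6.8). It adds that each subject's "slit lamp biomicroscopy information will be presented in" Listing 16.2.9.3.

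On the reference visit, SAP 5.1.7 says of the study-eye post-operative visits: "These data will be summarized in the same table for each active dosing regimen and its matching vehicle placebo", and "The Pre-dose assessment at POD1 will be the baseline". It uses Screening as the baseline for the EOS comparison. SAP Table E labels Screening "Baseline for most safety endpoints".

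The only departure listed in SAP 6.6 begins "Added analyses for ACC grade at PODs 4, 8, 15 (and 22 for Part A".

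**The concern.** All subjects are examined the day after cataract surgery, when some inflammation is expected, and most should then improve. The tolerability question is how many subjects move the other way on study drug, and whether that number differs between active and vehicle. Grade frequencies at each visit describe each arm at each time but do not link a subject's later grade to that subject's baseline. Some worsening can therefore be offset by improvement in other subjects of the same arm.

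At stake is a within-subject safety endpoint that the protocol names for a product being given to humans for the first time (Protocol 1.4.2). As planned, it would reach the study report without a count by arm, and a reader of the SAP would not learn that the endpoint's form had changed.

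**Working it through.** The plan states no figure on this point to reproduce. The check is a comparison of text, followed by an illustration.

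**1. Protocol against SAP.**
- Protocol synopsis and Table 4: change from baseline in the three signs, as its own bullet.
- SAP 1.2 and 5.6: the signs are present, their change from baseline is not.
- SAP 5.1.8 defines change from baseline in general. SAP 5.6.7 does not use it.
- SAP 6.6 and the SAP Appendix: no entry on these signs. The Appendix does add comparisons of IOP change from baseline.
- Elsewhere the SAP refers safety data to baseline: laboratory shifts (5.6.3), IOP change and bands of IOP increase (5.6.5), visual acuity worsening (5.6.6).

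**2. What by-visit frequencies determine.** Let n(i,j) be the number of subjects with baseline grade i and visit grade j, with grades 0 to 3. The planned table gives the totals over j (baseline frequencies) and over i (visit frequencies). The number worsened is W = sum of n(i,j) over j > i. The totals usually fix only a range for W, found by minimising and maximising W subject to them.

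Inputs: 21 subjects per arm (SAP Section 3). The grade counts are assumed, because the documents give none.

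Main case, absent/mild/moderate/severe from 5/9/6/1 at POD1 to 14/5/2/0 at a later visit:
- Minimum: 5 absent stay absent; 9 mild become absent; of 6 moderate, 2 stay and 4 become mild; 1 severe becomes mild. Result 14/5/2/0 with W = 0 (14 improved, 7 unchanged).
- Maximum: 5 absent become mild; 2 mild become moderate; the other 7 mild, 6 moderate and 1 severe become absent. Result 14/5/2/0 with W = 7 (14 improved, 0 unchanged). W cannot exceed 7, because only 5 + 2 = 7 subjects are above absent at that visit.

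So the same table fits 0/21 = 0% to 7/21 = 33%. Each subject is 1/21 = 4.8 percentage points.

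Other assumed cases:

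| Baseline | Visit | Range of W |
|---|---|---|
| 5/9/6/1 | 5/9/6/1 | 0 to 12 |
| 5/9/6/1 | 10/7/3/1 | 0 to 9 |
| 2/8/9/2 | 12/6/2/1 | 0 to 5 |
| 5/9/6/1 | 2/8/9/2 | 4 to 16 |
| 5/9/6/1 | 21/0/0/0 | exactly 0 |

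The fourth row shows that net deterioration of an arm does appear: the lower bound rises above zero. The last row shows that complete clearing leaves no doubt. In the other rows the count is undetermined.

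**3. Other routes to the count.** Listing 16.2.9.3 holds each subject's grades but gives no total and no comparison of arms. Protocol 7.3.1 makes clinically relevant deterioration an adverse event. However, Protocol 8.1 keeps events that the investigator considers normal for cataract surgery in the source documents only, and Protocol 1.4.1 lists corneal edema and ciliary and conjunctival hyperemia among the commoner post-surgical reactions. The adverse event route is therefore partial.

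**The case against.** The strongest defence is that the SAP carries out the analysis the protocol planned. Section 10.3.3 asks for change from baseline for IOP and for worsening of visual acuity, and the SAP provides both. For slit-lamp results it asks only for a categorical summary, and SAP 5.6.7 repeats that. On this view nothing was removed that SAP 6.6 needed to declare. Part of this stands: the inconsistency begins inside the protocol, between Table 4 and 10.3.3. It does not close the gap. A shift table is itself a categorical summary, so it would satisfy both sections, whereas by-visit frequencies satisfy only 10.3.3.

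A reader might also infer that the SAP has dropped the endpoint, or that worsening cannot be seen at all. The documents do not support either. The signs remain safety endpoints and are tabulated by grade, arm and visit. POD1 and later visits share a table, so net change in each arm is readable against vehicle. Individual grades are listed, and clinically relevant deterioration outside normal surgical expectation is reported as an adverse event.

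The size can be pushed too far as well. With 7/7/7 (absent/mild/moderate) at both visits, up to 14 of 21 subjects could have worsened, but that needs every absent and mild subject to worsen and every moderate one to clear. In a randomized comparison, an active-arm excess of worsening is masked only if the same arm also has an offsetting excess of improvement.

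Finally, this is a Phase 2a study with no formal hypotheses, and Table 4 does not ask for a between-arm difference or confidence interval. That stands, and those items are optional.

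**Conclusion.** The concern holds in a limited form. The protocol lists change from baseline in the three ocular signs under its primary safety objective. The SAP text plans no summary of that change and does not say so. What is missing is the count by arm of subjects who worsened; the data and the group-level picture are not missing. Under the assumed improving distribution, that count is left anywhere between 0 and 7 of 21. The range depends entirely on the assumed grades and is not an estimate of harm. No sample size, power or significance level is affected.

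Two limits apply. The SAP's table list and shells are not shown, so the content of Tables 14.3.6.6 to 14.3.6.8 is read from the text of 5.6.7. The baseline also needs to be named, because Table E and SAP 5.1.7 can be read differently; taking POD1 as the reference for every visit would conflict with the Screening baseline that 5.1.7 sets for EOS.

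**What to change.** In SAP 5.6.7 (Tables 14.3.6.6 to 14.3.6.8), for each sign and each active/vehicle pair, add a shift table from baseline grade to each visit. Under it, give the numbers improved, unchanged and worsened by at least 1 grade, among subjects with both assessments. Use POD1 pre-dose as baseline for the study-eye post-operative visits and Screening for EOS, as in SAP 5.1.7, and state this in the table.

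Restore the change-from-baseline wording in SAP 1.2 and 5.6. An active-minus-vehicle difference in the worsened proportion with an exact confidence interval is optional and would be descriptive only.

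The cost is SAP wording and one added block in three tables; every grade needed is already scheduled for collection. The SAP Appendix already quotes exclusion counts for 132 subjects, so the addition should be documented as such. It is not a data-driven choice, because the endpoint is in the protocol.

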Cataracts	
The lens structure and posterior capsular opacification (POC) in the study eye will be monitored at each clinic visit throughout the study. The lens in the non-operated eye will be evaluated at Screening, EOS and Early Termination visits.
	
Based on data from studies of dermal products of CP, use of APP13007 may result in posterior subcapsular cataract formation in the non-operated eye. While the risk is likely to be small, this cannot be quantified because the extent of CP systemic exposure in humans following ocular instillation of APP13007 is not known.

Delayed Healing	
Subjects with thinning of the cornea or sclera are excluded because of the greater risk of perforations with the use of topical steroids.
 
Protocol includes stopping criteria for study drug if the Investigator, in consultation with the Study Medical Monitor, is concerned about delayed healing.
	
Use of APP13007 may delay healing after cataract surgery and increase the incidence of bleb formation.

Risk of Infection	
Subjects with on-going ocular bacterial, viral or fungal infections are excluded from the study.
 
Ocular infections occurring during the study should be assessed and treated appropriately.
 
The Investigator should discuss with the Study Medical Monitor whether to stop study drug if ocular infection occurs.
	
Use of APP13007 may suppress the host immune response and increase the hazard of ocular infections. This risk is likely to be low based on potential low systemic CP exposure and data from studies of other steroids products approved for the treatment of inflammation and pain after ocular surgery.

Hypothalamic-Pituitary-Adrenal	Monitor for symptoms and signs of reduced adrenal function	Systemic absorption of topical corticosteroids can produce

Potential Risk	Management	Comments

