7.3.3. Slit Lamp Biomicrocopy

The number of anterior chamber cells will be counted twice and anterior chamber flare assessed as described in Section 7.2.1.

In addition to the assessment of the anterior chamber cells and flare, the following parameters will be evaluated using the following scales during the slit lamp exam:

Bulbar Conjunctival Injection

Grade	Description
0	Absent
1	Mild
2	Moderate
3	Severe

Sclera - Ciliary Flush

Grade	Description
0	Absent
1	Mild
2	Moderate
3	Severe

Corneal Edema

Grade	Description
0	Absent
1	Mild
2	Moderate
3	Severe

Lens Pathology (in the contralateral/non-surgical eye) will be evaluated as:

- Normal; no opacity in the lens
- Abnormal; existing opacity in the lens; aphakic or pseudophakic eyes or other abnormal findings.

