7.3.5. Dilated Ophthalmoscopy

A dilated fundus examination will be performed according to the Investigator's standard technique and will occur as indicated in the Schedule of Events (Table 2A or Table 2B). The Investigator should evaluate the vitreous, retina, macula, choroid, and optic nerve with cup/disc ratio and will note normal/abnormal findings.

The Investigator will determine whether or not abnormalities observed at the Screening visit would exclude a subject from study participation.

If a subject has a cataract in the non-operated eye at the Screening visit, the Investigator should make an assessment whether there has been a change in the size or composition of the cataract at the EOS/POD28 visit (Part A) or EOS/POD22 visit (Part B) or at early termination. This information will be recorded in the source document and eCRF.

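### Lens and fundus findings are tabulated as unpaired Screening and EOS counts, and the investigator's recorded judgement of cataract change has no named summary, so the number of individual eyes that worsened cannot be read from the tables

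*SAP*

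**What the plan says.** The risk is named in the protocol. Table 3 (Risk Mitigation Plan, Cataracts row) states that "use of APP13007 may result in posterior subcapsular cataract formation in the non-operated eye". It expects the risk to be small but says it cannot be quantified.

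The protocol describes two lens observations in the non-operated eye:

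- A normal/abnormal classification at slit lamp (7.3.3), in which the second category reads "Abnormal; existing opacity in the lens; aphakic or pseudophakic eyes or other abnormal findings".
- A within-subject judgement. If a cataract was present at Screening, the investigator is to "make an assessment whether there has been a change in the size or composition of the cataract at the EOS/POD28 visit" in Part A, at POD22/EOS in Part B, or at early termination (7.3.5; 6.2.6 repeats the instruction for EOS). Section 7.3.5 adds: "This information will be recorded in the source document and eCRF".

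SAP 5.6.7 plans Table 14.3.6.15 for the non-study-eye lens, "for subjects with phakic lens by the total number of subjects with abnormal findings and by abnormal cataract category" (nuclear, cortical, posterior subcapsular) "and by cataract Grade 1, 2, and 3 for each active dosing regimen and its matching vehicle placebo at Screening and EOS visits". Tables 14.3.6.9 to 14.3.6.13 give the number of subjects with abnormal vitreous, retina, macula, choroid and optic nerve at Screening and EOS. On listings, the section says: "All dilated indirect ophthalmoscopy ocular exam data will be presented in" Listing 16.2.9.4.

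Neither SAP 5.6.7 nor the SAP Appendix names a summary of the investigator's change judgement, or a Screening-to-EOS shift for lens or fundus.

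**The concern.** The safety question is within-subject: in how many eyes did a finding appear or worsen between Screening and EOS, by arm? Separate counts at two visits do not answer it. Gains in some eyes can be offset by losses in others, through grader variability. Because safety data are summarised as observed without imputation (SAP 5.1.6.2 and 5.6), the two counts may also rest on different subjects.

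The one item the protocol collects as an explicit within-subject lens assessment is the investigator's judgement of change, and it has no named place in the tables. The SAP does use within-subject summaries for other safety data: laboratory shifts (5.6.3), IOP change with Screening as baseline for EOS (5.6.5), and acuity worsening at EOS from Screening (5.6.6). It gives no reason for treating lens and fundus differently.

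At stake is whether the report of the first human study of APP13007 can state, for a risk the protocol names, how many eyes developed or worsened a lens opacity in each arm.

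**Working it through.** The plan gives no figure for lens change, so there is none to reproduce. The check asks what the planned counts can and cannot determine.

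**Inputs.** Arm size of 21 is from SAP section 3. All counts by grade below are assumed for illustration, with the same 21 eyes at both visits.

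**Method.** Consider every Screening-by-EOS cross-table compatible with the two sets of counts. Find the smallest and largest number of eyes that moved to a higher grade.

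1. *Normal/abnormal row alone, 3 normal and 18 abnormal at both visits.* Newly abnormal eyes number at least max(0, 18 − 18) = 0 and at most min(3 normal at Screening, 18 abnormal at EOS) = 3. The row says nothing about worsening within the eyes already abnormal.

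2. *Grade counts none/1/2/3 of 3/8/7/3 at both visits.*
   - Minimum: 0.
   - Maximum: upward arrivals can be at most 3 in Grade 1 (only the 3 ungraded eyes can rise into it), 7 in Grade 2 and 3 in Grade 3. The total is 3 + 7 + 3 = 13, and a cross-table achieving it exists.
   - If recorded grades never fall, identical counts force 0.

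3. *Grade counts moving from 3/8/7/3 to 3/5/8/5.*
   - Eyes at Grade 2 or above go from 7 + 3 = 10 to 8 + 5 = 13, so at least 3 eyes worsened.
   - Maximum: 3 + 8 + 5 = 16 by the same arrival count.
   - If grades never fall, 3 eyes cross from below Grade 2 to Grade 2 or above, and 5 − 3 = 2 cross into Grade 3. Worsened eyes then number 3 (if 2 of them cross both thresholds) to 3 + 2 = 5.

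4. *Fundus structures, abnormal only, for example 3 abnormal and 18 normal at both visits.* Newly abnormal eyes number from max(0, 3 − 3) = 0 to min(18, 3) = 3. There is no category or grade to narrow this.

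| Assumed counts, n = 21 | Eyes worsened, grades may fall | Grades cannot fall |
|---|---|---|
| Lens grade unchanged, 3/8/7/3 | 0 to 13 | 0 |
| Lens grade 3/8/7/3 to 3/5/8/5 | 3 to 16 | 3 to 5 |

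The grade rows therefore do reveal net progression (example 3 cannot be read as no change), but not how many eyes progressed. EOS examinations missing for some subjects would widen every range.

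One qualification on the grade rows: the protocol defines lens pathology only as normal or abnormal, and neither document defines cataract Grades 1 to 3.

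**The case against.** The strongest answer is that the plan covers lens safety by several routes.

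- Table 14.3.6.15 does more than count abnormal lenses. It is limited to phakic eyes, which removes the aphakic and pseudophakic eyes that the protocol scale calls abnormal, and it adds category and grade. Posterior subcapsular cataract, the named risk, has its own category.
- Protocol 7.3.1 makes any clinically relevant deterioration an adverse event, and SAP 5.6.2 summarises ocular events in the non-study eye by relationship and severity.
- Listing 16.2.9.4 shows the ophthalmoscopy data by subject. With about 21 per arm, a reader can trace individual eyes.
- Missing EOS examinations should be few. Assumed dropout is 5%, withdrawn subjects get EOS assessments on both eyes (protocol 6.2.7, 6.4), and rescued subjects get the EOS ophthalmoscopy (SAP Tables C1 and C2).
- SAP 5.6.7 says ophthalmoscopy findings will be summarised categorically, which does not exclude the change item. Table titles are not visible in the supplied text.

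Most of this stands and limits the impact. It rules out three stronger conclusions that a reader might draw. The first is that progression in eyes already abnormal at Screening is invisible; the category and grade rows show net movement. The second is that the tables could conceal an unlimited number of new findings; the ranges are bounded, and with unchanged grade counts the number is zero if grades do not fall. The third is that the report would show no lens or fundus signal whatever happened; adverse events and listings contradict that. Nor can one state what share of progressions the normal/abnormal row would miss, because the documents give no Screening prevalence of fellow-eye opacity.

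What the objection does not remove is that no named table gives the number of eyes changed by arm. A listing is not a comparison, adverse events depend on a judgement of clinical relevance, and the change item is mentioned nowhere in the SAP.

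**Conclusion.** The point holds as a modest gap in presentation. Lens and fundus findings are planned as unpaired counts at Screening and EOS, and the investigator's recorded judgement of cataract change has no named summary. Net shifts in lens category or grade will be visible; the number of individual eyes with new or worsened findings will not. In the illustrations that number spans 0 to 13 or 3 to 16 of 21 eyes if recorded grades can fall, and 0 or 3 to 5 if they cannot. These ranges rest on assumed counts and complete pairing.

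Severity is low. The data are descriptive safety data in an exploratory Phase 2a study with 14 or 21 days of dosing, the protocol links this risk to prolonged use (1.4.1) and expects it to be small, and adverse event reporting and listings give partial cover. The improvement is still worth making because it uses data already collected and answers the question the protocol raises. Whether Listing 16.2.9.4 includes the change item is not stated.

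**What to change.** In SAP 5.6.7, by arm:

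1. Add to Table 14.3.6.15 the number of eyes judged changed in size or composition, among those with a Screening cataract and an EOS or early-termination examination.
2. Add a paired Screening-to-EOS shift by cataract category and grade, with new or higher-grade posterior subcapsular cataract shown separately.
3. Add to Tables 14.3.6.9 to 14.3.6.13 the number of subjects normal at Screening and abnormal at EOS, with the number examined at both visits as denominator.

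The cost is a few table rows and a paragraph of SAP text. It needs no new data and no change to visits or conduct. If the tables have already been run, the rows can be produced as additional output and documented in the study report under SAP 5.1.11.
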